PRO	Patient Reported Outcome
PSUR	Periodic Safety Update Report
QPPV	Qualified Person Responsible For Pharmacovigilance
QRP	Quality Review Plan
SAE	Serious Adverse Event
SAP	Statistical Analysis Plan
STROBE	Strengthening the Reporting of Observational Studies in Epidemiology
WHO DD	World Health Organization Drug Dictionary

3. Responsible parties

Research question and objectives	
The primary objective of the study is:
 
 • To evaluate changes in pain, functions in daily living, and OA related quality of life for an observation period up to 64 weeks 
The secondary objectives in this study are:
 
 • To assess drug utilization with Theraflex® for an observation period up to 64 weeks period • To assess patients satisfaction with Theraflex® treatment for an observation period up to 64 weeks • Description of the use of analgesics for OA for an observation period up to 64 weeks

	
 • Description of patient characteristics (Age, BMI, Weight, Analgesics intake)
Study design	Open-label, multicenter, single country, non-interventional prospective study in a cohort of patients with Hip or Knee OA stage I to III who started a treatment with Theraflex® with evaluation of health status by physical examination and validated patient and physician's questionnaires for an observation period up to 64 weeks
Population	Male and female patients from 45 to 75 years of age with hip or knee osteoarthritis stage I to III. Approximately 1100 subjects are planned to enrolled in the study in about 60 study centers in Russia.
Variables	
Variables to determine the primary endpoint(s)
 
 • Changes in pain, other symptoms, functions and knee related quality of life assessed by KOOS in patients with knee OA • Changes in pain, others symptoms, functions and hip related quality of life assessed by HOOS in patients with hip OA 
Variables to determine the secondary endpoint(s):
 
 • Drug utilization of Theraflex® therapy as reported by the patient to their physician • Patient satisfaction measured with a Likert response scale (from 5 – very satisfied to 1-very dissatisfied) • Type, frequency and length of painkiller for the symptomatic treatment of hip OR knee OA for an observation period up to 64 weeks • Other medication/physical therapy for OA related pain (drugs, duration of use, dose, frequency)
Data sources	The investigator collects historic data (demographic and clinical characteristics) from medical records if available. Likewise, the investigator collects treatment related data during visits that take place in routine practice. Each patient is identified by a unique central patient identification code, which is only used for study purposes. For the duration of the study and afterwards, only the patient's treating physician or authorized site personnel is able to identify the patient based on the patient identification code.

Study size	It is planned to enroll approximately 1100 patients into the study.
Data analysis	
All variables will be analyzed in an exploratory manner with appropriate descriptive statistical methods: categorical variables by frequency tables (absolute and relative frequencies) and continuous variables by sample statistics (i.e. mean, standard deviation, minimum, median, quartiles and maximum).
 
Statistical analyses will be performed using validated statistical software (e.g. SAS, SAS Institute Inc.).

Milestones	
Planned start of data collection – Oct, 2017
 
FPFV –Oct 2017;
 
LPLV –Feb 2020;
 
end of study –May 2020

5. Amendments

Table 1: Amendments

Amendment Number	Reason for Amendment	New version number	Effective Date
1	
Correction of exclusion criteria was conducted, since it became obvious that with initial exclusion criteria slow patient recruitment is predictable
 
The approach for completing the questionnaire was clarified in case the patient has multiple joint OA or bilateral Knee/Hip OA.
 
Requirements for collection of vital signs and data of physical examination were clarified.
 
Information about the Independent Ethics Committee responsible for protocol related documentation review and approval was updated
 
The number of patients is reduced from 1500 patients to 1100 patients.
	2,0	17-Nov-2017
2	
Originally planned to conduct an observational study of the Theraflex product in 80 study centers of Moscow, St. Petersburg and Yaroslavl regions. In connection with the additional administrative barrier on the part of the Moscow Health Care Department, instead of 40 centers planned for opening in the Moscow region, the number of study centers in Moscow has dropped to 20. Thus, the total number of study centers will not exceed 60, which is 75% of the planned number of clinical centers. In proportion with reduced number of study centers, the number of patients in the study is also reduced by 25%, which in numerical terms approximately corresponds to 1100 patients.
 
In order to calculate the indicator of “patients lost to follow-up subjects”, was made a simple analysis of the V2 frequency on the group of the first 10% of subjects included into the study. The analysis was carried out after 3-6 months from the date of patients recruitment, which corresponds to allowable time-window for the second visit. As a result of this analyses, “patients lost to follow-up” index is about 7%, which is significantly lower than initially assumed figure for this indicator (In the Study Risk Register this risk factor was registered as 20% and above). This additionally makes possible to reduce the study population to
	3.0	4-Jul-2018

	
1100 subjects without negative effect on the result of the whole study.
 
Since the analysis of all variables in the study will be carried out using appropriate methods of descriptive statistics, a decrease in the number of patients cannot have a negative impact on the representativeness.
 
Initially It was planned to have interim analysis after all subjects have completed V2. With this amendment the starting point is changing – Interim analysis will be conducted after 50% of subjects (first 550 enrolled) have completed V2 in order to assess the changes after the first course at the half of the study population..
		
--	---	--	--

6. Milestones

Definitions:

- Start of study: FPFV
- Start of data collection: date of first data entry in database
- End of data collection: date of last data entry in database
- End of study: date of clean database
- Observation period: time-window for data collection
- Final report: final report of study results 12 months after clean database

7. Rationale and background

In the recommendations of The Osteoarthritis Research Society International (OARSI) and The European League Against Rheumatism (EULAR), all therapeutic agents for Osteoarthritis (OA) treatment are classified to non-pharmacological, pharmacological and invasive treatments, which can have not only symptom-modifying, but also structure-modifying effects on the basis of their ability to positively influence disease progression (Zhang W. et al., 2008). Structure-modifying medications for OA treatment are those whose actions are based on anabolic processes activation in cartilage matrix, suppression of lysosomal enzymes and stimulation of chondrocyte functions (Jerosch J., 2011). Slow-acting drugs (glucosamine, chondroitin, hyaluronic acid, diacerein, unsaponifiable matters of avocado and soya) exert a delayed effect that lasts beyond discontinuation. These therapeutic agents possess not only symptomatic effects, but also, probably, may retard the OA progression, having an influence on several pathogenesis links of the disease (Zhang W. et al., 2008).

The demonstrated efficacy of glucosamine (Gl) and chondroitin sulfate (Ch) in form of mono-medication in several studies created the necessary prerequisites for combined therapy (Qiu GX., et al., 2005, Zegels B., 2013). It was shown in an experimental model, that combination of chondroitin sulfate and glucosamine increased chondrocyte production of glycosaminoglycans by 96,9% versus 32% in case of an administration of chondroitin sulfate or glucosamine alone (Lippiello L. et al., 1999). The GAIT trial studying the impact of glucosamine (500 mg 3 times daily) and chondroitin sulfate (400 mg 3 times daily) on the joint space narrowing progression

in gonarthrosis have shown higher potential of clinical effect predominantly in the II radiological stage (Kellgren/Lawrence) in comparison with the III one in the subgroup of patients with moderate-to-severe knee pain (Clegg DO. et al., 2006). Moreover, the authors focused attention on good safety profile of the therapy that was comparable with placebo administration (Sawitzke, 2010). According to Lapane KL. et al., about a half (47%) of patients over 49 years with radiographic knee OA use additional medicines and about a quarter (24%) combined additional and conventional (predominantly NSAIDs) medications. The most popular additional medicines were glucosamine and chondroitin: more than 55% used these products alone or in combination (Lapane KL. et al., 2012). Investigators of the University of Queensland (Australia), have found out while questioning of patient of 27-95 years old with knee and hip joints OA, that for the purpose of pain relief and joint function improvement most frequently used medications are those containing GL and Ch (51% of males and 60% of females) (Ng NT. et al., 2012).

Up to 30% of OA patients over 55 years in UK don't receive an adequate therapy of chronic pain syndrome (McAlindon TE. et al., 1992). Chronic pain in OA leads to shortening of patient life duration by an average of 10 – 12 years (Nuesch, Dieppe, & Reichembach, 2011..) Chronic disability in OA leads to an 2.4 times increase in mortality (hazard ratio 3.91) but in association with multi-morbidity in 4 times (hazard ratio 3.91) compared with general population (Landi F. et al., 2010).

Russian Ministry of Health recommends to use only NSAIDs ("The Standard of Primary Health Care in Gonarthrosis and Similar Clinical Conditions", 2012). However, in Russia a variety of medicinal products from chondroprotectors category are widely recommended by physicians and the majority of leading scientific experts consider this treatment as effective as a part of the complex therapy. This fact was reflected in the recently published "Recommendations for the Treatment of Patients with Osteoarthritis with Comorbidity in Clinical Practice of GPs", 2015. This document, prepared by Russian Scientific Society of GPs and Association of Russian Rheumatologist, compiled by 100 main Russian experts from different regions, affirms, that a complex OA therapy should include symptomatic slow acting drugs and the best clinical results would be obtained with the combination of Gl and Ch.

Thus, the long-term prospective observational study in subjects with knee or hip OA, who receive Theraflex®, will allow to obtain valuable information in respect of dynamics of pain syndrome, functions of living, quality of life and satisfaction of patient as well as of actual drug utilization by patients with OA for an observation period up to 64 weeks.

Use of Gl and Ch is widespread among OA patients worldwide, however since in Russia at the present time there are no standards approved by Regulatory Authorities for the management of patients with OA, we expect that this study will help to evaluate the approach of doctors to the treatment of OA and to understand the role of Theraflex® within the therapeutic algorithm in the context of routine clinical practice.

8. Research questions and objectives

8.1 Primary objective

The primary objective of the study is:

- To evaluate changes in pain, functions in daily living, and OA related quality of life for an observation period up to 64 weeks

8.2 Secondary objectives

The secondary objectives in this study are:

- To assess drug utilization with Theraflex® for an observation period up to 64 weeks
- To assess patients satisfaction with Theraflex® treatment for an observation period up to 64 weeks
- Description of the use of analgesics for OA for an observation period up to 64 weeks
- Description of patient characteristics (Age, BMI, Weight, Analgesics intake at baseline)

9. Research methods

9.1 Study design

[figure not shown]
This is a company sponsored, single country, open-label multicenter non-interventional prospective study in a cohort of patients with Hip or Knee OA stage I to III who started a treatment with Theraflex® with evaluation of health status by physical examination and validated patient and physician's questionnaires for an observation period up to 64 weeks.

There are up to 4 study visits planned: within two weeks after starting the Theraflex® treatment subjects will be included into the study in the initial study visit if they meet all inclusion criteria and none of the exclusion criteria. The initial visit is followed by two follow-up visits and final end of observation visit for an observation period up to 64 weeks. If patient switches to another Gl and Ch brand the observation of the patient is terminated.

During all visits data generated during the normal clinical practice will be collected by the investigator. In addition the patient reported outcome assessing Knee or Hip osteoarthritis outcome will be collected at the time of the visit as well as a simple patient satisfaction questionnaire.

For Knee OA the Knee injury and Osteoarthritis Outcome Score (KOOS) will be used. For Hip OA the Hip Osteoarthritis Outcome Score (HOOS) will be used (See section 9.3.3.8)). To reduce the number of questions and the burden of the patient, the physical short form of both patient reported outcomes (PRO) (KOOS-PS, HOOS-PS) containing reduced number of questions replaces the two subscales functions "daily living" and "functions, sports and recreational activities"

Figure 1: Study Overview

*start of treatment occurs after purchase of the product at the pharmacy (self-selection)

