9.2.7 Visits

The investigator documents an initial visit, follow-up visits and the end of observation/final visit for each patient in the case report form (CRF). Follow-up visits occur during routine practice, the study protocol does not define exact referral dates for those visits. The end of

observation/final visit is to be documented for a period up to 64 weeks after start of the initial treatment.

The observation period for each patient is up to 64 weeks. If patient switches to another Gl and Ch brand the observation of the patient is terminated.

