9.2.7.3 Follow-up Visits I & II

Follow-up visit will be the first visit at the physician during the time frame week 16-24 (Follow-up I), week 36-44 (Follow-up II), after start of treatment with Theraflex®. If patient switches to another Symptomatic Slow-Acting drug in Osteoarthritis (SYSADOA), the observation of the patient is terminated.

During the follow-up visit the investigator conducts all examinations according to the local routine clinical practice. In addition the investigator provides to the subject the PRO

questionnaire and the overall satisfaction question for completion. The patient needs to assess the outcome of joint treatment, which was selected as the “target” at the first visit.

Following information will be captured in the CRF:

- Date of visit
 - day, month, year
- Physical Examination
- Weight (kg)
- Vital Signs
 - Blood Pressure
 - Body Temperature (axillary temperature)
 - Heart rate
- Review of Theraflex® drug utilization
 - Start / End of treatment
 - Dose/frequency of treatment
- KOOS or HOOS Questionnaire (PRO)
- Patient satisfaction with Theraflex®
- Concomitant medication
- Concomitant disease(s)
- Concomitant non- medication therapies (e.g. physiotherapy, surgery)
- Adverse events

All examinations are performed according to the local routine institutional practice as indicated by the attending physician. PRO should be completed at the time of the visit at the physician by the patient.

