9.2.7.4 Final Visit / End of Observation

Final Visit / End of Observation will be the first visit at the physician’s office after an observation period up to 64 weeks after start of treatment with Theraflex®. Final visit should be performed during the time frame week 56-64

During the visit the investigator conducts all examinations according to the local routine clinical practice. In addition the investigator provides to the subject the PRO questionnaire and the overall satisfaction question for completion. The patient needs to assess the outcome of joint treatment, which was selected as the target at the first visit.

Following information will be captured in the CRF:

- Date of visit
 - day, month, year
- Physical Examination
- Weight (kg)
- Vital Signs
 - Blood Pressure
 - Body Temperature (axillary temperature)
 - Heart rate
- Review of Theraflex® drug utilization

- Start / End of treatment
- Dose/frequency of treatment
- KOOS or HOOS Questionnaire (PRO)
- Patient satisfaction with Theraflex®
- Concomitant disease(s)
- Concomitant non-medication therapies (e.g. physiotherapy, surgery)
- Adverse events

All examinations are performed according to the local routine clinical practice as indicated by the attending physician. PRO should be completed at the time of the visit at the physician by the patient.

Premature end of therapy does not automatically imply end of documentation: the patient should be followed up until the end of the observation period (64 weeks) or until no longer possible.

Table 2: Tabulated overview on variables collected during the study

	Prior to inclusion to the study	Visit 1 Inclusion into the study	Visit 2 & 3 Follow-up visit	Visit 4 Final Visit / End of Observation
		First Visit after starting treatment with Theraflex® [not more than 2 weeks]	Week 16-24 Week 36-44 after start of treatment with Theraflex®	Week 56-64 after start of treatment with Theraflex®
Assessment of inclusion / exclusion criteria		X		
Information about the study	X			
Written Informed Consent		X		
Patient demographic data		X		
Physical Examination*		X	X	X
Height /Weight**		X	X	X
Vital signs		X	X	X
OA Staging according to Kellgren & Lawrence*		X		
Lifestyle		X		
Concomitant therapies other than drug		X	X	X
Medical history /concomitant diseases		X	X	X

Concomitant medication		X	X	X
Adverse events		X	X	X
Review of Theraflex® drug utilization		X	X	X
KOOS or HOOS Questionnaire (PRO)		X	X	X
Patient satisfaction (PRO)		X	X	X

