9.3.3.14 End of observation

If available the primary reason for end of observation/study discontinuation should be stated:

- Regular end of observation
- Patient lost to follow up
- Consent withdrawn by patient
- Investigator decision
- (Serious) Adverse Event/Adverse Drug Reaction
- Pregnancy
- Lack of efficacy
- Patient died
- Change to another GI+Ch therapy (which therapy and reason for switch)
- Site closed
- Study terminated

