7.2. Missing data

The per protocol analysis is planned to be performed using available data only with no missing data replacement methods. The exception will be incomplete dates for separation of prior and concomitant treatments, as well as for separation of AEs occurred during the study and AEs occurred prior to the initiation of the study (incomplete dates will not be replaced with any data during classification).

Prior/concomitant therapy with missing or incomplete dates of start and end of the event

Table 7.2:1 - Classification algorithm for prior, concomitant and post-treatment therapies with missing or incomplete dates of start and end of the event

Start date	End date	Actions
Known	Known	To be considered as prior therapy, if the end date is < the start date of the study drug To be considered as concomitant therapy, if the end date is >= the start date of the study drug and the start date is <= the end of treatment To be considered as post-treatment therapy, if the end date is >= the start date of the study drug and the start date is > the end of treatment
	Partially missing	The end date should be replaced with the latest date possible (i.e. the last day of the month, if the day is unknown, or December 31, if the day and the month are unknown), then: To be considered as prior therapy, if the end date is < the start date of the study drug To be considered as concomitant therapy, if the end date is >= the start date of the study drug and the start date is <= the last administration date To be considered as post-treatment therapy, if the end date is >= the start date of the study drug and the start date is > the end of treatment
	Missing	The event should not be considered as prior, if the end date is missing To be considered as concomitant therapy, if the start date is <= the last administration date To be considered as post-treatment therapy, if the start date is > the end of treatment

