**IMPACT No. 19649 STATISTICAL ANALYSIS PLAN v.2.0 13 JUL 2020**

- Frequency and shift tables based on the results of the scale assessment [*very dissatisfied, dissatisfied, neither satisfied nor dissatisfied, satisfied, very satisfied*] presented overall and separately for patients with knee and hip osteoarthritis;
- Descriptive statistics for results and changes from Visit 1 (as the Likert scale data are best described by the median, not the mean, 95% CI is additionally provided for the median).
- Use of analgesics for symptomatic treatment of osteoarthritis:
 - Data will be presented on the patient's additional analgesic treatment of pain in the target joint (no/occasionally/regularly, topical agents/systemic agents/combined treatment) at the time of starting the chondroprotector (Theraflex/Theraflex Advance), at the time of study completion, as well as the investigator's assessment of the dynamics of the analgesic treatment of pain in the target joint from the start of the chondroprotector (Theraflex/Theraflex Advance) until the patient's discontinuation from the study (not changed/increased/decreased/pain treatment was discontinued) and time until complete cessation of analgesic treatment (1 month/ 2 months/ 3 months/ 6 months/ 12 months after the start of the chondroprotector), if it was completely discontinued;
 - Tables similar to those described in section 8.5 will be presented by pharmacological subgroup (3rd level) and chemical subgroup (4th level) for various indications [Symptomatic treatment with analgesics for target joint OA/ Other medication for target joint OA related pain/ Other therapy for target joint OA];

Individual subject data will be presented in listings.

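### Patients who switch product leave observation with no required satisfaction rating, so the later satisfaction percentages describe only patients still observed and may be too favourable

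*Protocol*

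**What the plan says.** Satisfaction with Theraflex over up to 64 weeks is a secondary objective (Protocol 8.2) and a secondary endpoint (9.1.2). It is one five-point question, answered at the physician visit (9.3.3.9). Table 2 schedules it at Visits 1 to 4 only: within two weeks of starting treatment, then weeks 16-24, 36-44 and 56-64.

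Two rules end observation on a switch:

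- Protocol 9.1, repeated in 9.2.7: "If patient switches to another Gl and Ch brand the observation of the patient is terminated".
- Protocol 9.2.7.3: "If patient switches to another Symptomatic Slow-Acting drug in Osteoarthritis (SYSADOA), the observation of the patient is terminated".

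When observation ends, 9.3.3.14 asks for the main reason, if available. One option is a change to another combination "therapy (which therapy and reason for switch"). Lack of efficacy, adverse event and loss to follow-up are separate options. No rating is requested there. For the last scheduled visit, 9.2.7.4 says: "Final visit should be performed during the time frame week 56-64".

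Stopping treatment is handled differently. Section 9.2.7.4 says: "Premature end of therapy does not automatically imply end of documentation", and asks that such patients be followed to the end of the observation period or for as long as possible.

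SAP 9.2 plans for satisfaction: "Frequency and shift tables based on the results of the scale assessment", together with descriptive statistics, changes from Visit 1 and a 95% CI for the median. SAP 7.2 describes the analysis as "using available data only with no missing data replacement methods".

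**The concern.** Patients choose and buy the product themselves, so changing to a competing product bears directly on satisfaction with this one. A rule that ends data collection at that event removes patients for a reason linked to the endpoint. A patient who switches at week 10, before the first follow-up window, contributes only a Visit 1 answer given in the first two weeks of treatment.

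The SAP sets no denominator for the satisfaction percentages, has no row for switchers and plans no sensitivity analysis. Protocol 9.9 (limitations) does not mention this selection. At stake is how the satisfaction objective is read. A figure for patients still observed at Visits 2 to 4 could be taken as a figure for everyone who started. The percentage satisfied could also rise between visits with no patient changing an answer.

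**Working it through.** **Who leaves the later tables**

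1. A switch ends observation. Which switches count depends on the section: another Gl and Ch brand in 9.1 and 9.2.7, any other SYSADOA in 9.2.7.3. The second set is wider, so the number removed depends on which text a site follows.
2. No section ties the satisfaction question to the switch, and the last scheduled question falls at weeks 56-64.
3. With available data only, a switcher is absent from every satisfaction table after the switch. Earlier answers are kept.
4. A patient who stops without switching is not covered by the rule and should still answer at later visits.

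**Size**

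The plan has no figure to reproduce: the study is descriptive and unpowered (Protocol 9.5), with no switch or satisfaction rate. The following is an illustration.

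- From the documents: planned enrolment N = 1100.
- Assumed: share switched before the visit, s = 2%, 5% or 10%; satisfied among stayers, p = 80%; satisfied among switchers, q = 80%, 50%, 20% or 0%. No other losses.

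Percentage over all patients = (1 − s)p + sq. Overstatement = p − [(1 − s)p + sq] = s(p − q).

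Example: s = 5%, q = 20% gives 0.95 × 80 + 0.05 × 20 = 77.0%, against 80% reported. The overstatement is 0.05 × 60 = 3.0 points.

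Sampling half-width = 1.96 × √(0.8 × 0.2 / n), with n = 1100(1 − s). This is a yardstick only; the SAP plans a CI for the median, not for the percentage.

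| Switched | n observed | q = 80% | q = 50% | q = 20% | q = 0% | Half-width |
|---|---|---|---|---|---|---|
| 2% (22) | 1078 | 0 | 0.6 | 1.2 | 1.6 | 2.4 |
| 5% (55) | 1045 | 0 | 1.5 | 3.0 | 4.0 | 2.4 |
| 10% (110) | 990 | 0 | 3.0 | 6.0 | 8.0 | 2.5 |

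The overstatement and half-width columns are in percentage points.

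Bounds that assume nothing about switchers run from (1 − s)p to (1 − s)p + s. With 80% observed, the figure over all patients lies within 78.4-80.4% at 2% switching, 76.0-81.0% at 5% and 72.0-82.0% at 10%.

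**Which tables can move**

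Take s = 10%, p = 80%, q = 20%, with every answer fixed over time. Before the switch the percentage is 0.9 × 80 + 0.1 × 20 = 74.0%. After the switchers leave it is 80.0%. The frequency table rises 6.0 points although nobody's opinion changed. A shift table pairs answers from the same patient, so an absent patient cannot create a transition in it. It too describes only patients still observed.

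**The case against.** **An end-of-observation visit may already cover switchers.** Protocol 9.2.7 says: "The investigator documents an initial visit, follow-up visits and the end of observation/final visit for each patient in the case report form (CRF". The SYSADOA rule also sits within the follow-up visit section, where the question is handed out. This has some force: a switch learned at a scheduled visit may well come with a rating. But no text ties that visit to the switch, and 9.2.7.4 times it at weeks 56-64. The CRF is not among the documents, so the fair statement is that a rating is not required, not that switchers are never asked.

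**The losses are already reported.** SAP 8.1 tabulates reasons for early withdrawal and the number of subjects at each visit, and SAP section 5 puts prematurely withdrawn subjects in the listings. That is true, but none of it is linked to satisfaction.

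**Switchers may be content.** Price or availability could prompt a switch, and lack of efficacy is a separate exit code. This stands: lower satisfaction among switchers is an inference.

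**Stronger readings the documents do not support.**

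- A reader might infer that everyone who leaves for lack of efficacy or an adverse event is also removed by rule. Only a switch ends observation by rule. The other two are possible exit reasons, and 9.2.7.4 keeps patients who merely stop under follow-up.
- A reader might use the 7% and 20% in Amendment 2 as leaving rates. Both are loss-to-follow-up figures, a category that 9.3.3.14 separates from switching. The 7% comes from the first 10% of subjects at Visit 2.
- A reader might take any improvement in the shift tables as an artefact of leavers. The paired structure rules that out.

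**Conclusion.** The structural point holds. Switchers leave the later satisfaction tables under a rule plausibly related to the endpoint, and the SAP neither shows nor allows for this. The Visit 2 to 4 percentages apply to patients still under observation and may be too favourable as statements about all who started.

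The direction rests on the assumption that switchers are less satisfied than stayers. The size is unknown. With an 80% versus 20% contrast, the bias passes the sampling half-width at about 4% switching (2.4 / 0.60 = 4.0%). With a smaller contrast or rarer switching it is minor, and with no contrast it vanishes. This is a secondary, descriptive endpoint, so the matter is one of presentation and interpretation. The two definitions of a switch contradict each other in any case and must be reconciled.

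**What to change.** **SAP 9.2.** At each visit, keep the percentage among those who answered and label it as applying to patients still under observation. Beside it, show the satisfaction distribution with all FAS patients as denominator, adding rows from the 9.3.3.14 reasons:

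- observation ended: change of product;
- observation ended: lack of efficacy;
- observation ended: adverse event;
- ended or missing: other.

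State that patients with Visit 1 data only count in this denominator. The FAS definition in SAP section 6 requires data after the start of the observation period and does not settle whether Visit 1 answers qualify.

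**Protocol 9.1, 9.2.7 and 9.2.7.3.** Reconcile the definition of the switch that ends observation, and state in the report which one was applied.

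**Optional, if data are still being collected.** Where a switch is learned at a visit, ask the satisfaction question about Theraflex once and label it early end of observation, not Visit 4. No such contact is guaranteed. KOOS and HOOS ask about the previous week, so a score taken after the switch should not be treated as a Theraflex outcome. The protocol planned the last visit for February 2020 and SAP version 2.0 is dated 13 July 2020, so this step may no longer be possible. The SAP change needs only data already collected.

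**Cost.** A few more table rows, and a percentage over all patients that will look somewhat less favourable. The optional step adds one question at a visit.
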